### 3.6. SAMPLE SIZE

According to the results of a previous trial that looked at a probiotic's effect on infants with CI, it is estimated that when the sample size in each group is 33, the study will have 80% power to detect an absolute difference of 35% in the treatment success rate (15% in the Placebo group and 50% in the treatment group) with a 0,05 alpha level.

The number of infants that will be included in the study is 80, with a dropout rate expected for a maximum of 20%.

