#### **Patient Baseline Characteristics**

Demographic and baseline characteristics will be summarized overall and by treatment group on the Intention To Treat population.

Demographic/diagnosis information includes:

- Sex

	Statistical Analysis Plan
	Sponsor:
	Protocol number:

- Age (days) at baseline will be computed in terms of days elapsed from birth date to informed consent date. When dates of parents' informed consent signatures are different, the latest date will be considered for the computation.
- Diagnosis of IC, according to Rome III criteria, for infants <= 4 months
- Type of childbirth (natural or caesarean)
- Gestational age (weeks) will be described by means of descriptive statistics for continuous data, while days will be only listed.
- Birth weight (g) will be described by means of descriptive statistics for continuous data, while its percentile will be only listed.
- APGAR 5 minutes score
- Positive family history of allergic diseases
- Exposure to second-hand tobacco smoke within the home environment
- Positive family history of functional gastrointestinal diseases
- Clinical/surgical history will be evaluated checking if the infant had any clinical/surgical relevant event in the past.

If the infant had a relevant event that could exclude him or her from the study, a category was required: ears/nose/throat, ophthalmic system, respiratory system, cardiovascular system, gastrointestinal system, hepatobiliary/pancreas, renal system, urogenital system, neurologic system, blood/lymphatic, endocrine/metabolic, musculoskeletal system, skin, psychiatric, other (allergies included). The frequency and proportion of patients who reported each category at least once will be summarized and presented by category, ATC Code Level 2 and Preferred Term. Patients could have more than one specification.

Other background characteristics will be evaluated at visit T0 and will include information about infant's parents:

- Number of terminated pregnancies of the mother
- Parents' smoking habit (if the father/the mother were smokers).

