### 6.5.1. Primary efficacy analysis

#### Treatment's success rate.

Duration of crying will be collected daily in the diary during the entire study period. The average daily duration will be defined as the mean duration of all cries recorded during the day in the “Evaluation of crying” section (i.e. sum of episodes’ duration/number of cries during the day).

Weekly mean will be defined as the mean of the calculated average daily durations during the selected week and will be described by means of descriptive statistics for continuous data. Mean changes from baseline (i.e. mean of the first Week) to the mean of the selected week will be computed as well.

Treatment success rate will be evaluated in terms of reduction of duration of cries, comparing mean weekly duration of the last Week (from T4 to T5) and mean weekly duration of Week 1 (from T0 to T1). A success will be defined as a reduction  $\geq 50\%$ .

The proportion of patients with a success in the two groups will be summarized by means of descriptive statistics for categorical data and analyzed by means of a Chi-Square test.

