### 6.5.2. Sensitivity analysis on primary endpoint

Not Applicable.

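### The primary chi-square test omits Week 1 crying, a pre-randomization value already collected; the test is valid, but some precision and protection against chance imbalance may be given up

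*SAP*

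**What the plan says.** SAP 6.5.1 finds each infant's reduction by "comparing mean weekly duration of the last Week (from T4 to T5) and mean weekly duration of Week 1 (from T0 to T1"), and sets the success threshold at 50% or more. The between-group comparison follows: "The proportion of patients with a success in the two groups will be summarized by means of descriptive statistics for categorical data and analyzed" by a chi-square test. The Protocol synopsis (Statistical methods) specifies the same test.

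No covariate or stratified test appears anywhere. SAP 6.5.2, on sensitivity analysis of the primary endpoint, reads "Not Applicable", and subgroup analyses (6.7) carry the same entry. SAP 3.2 describes a software-generated randomization list and mentions no stratification.

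Week 1 crying is available before treatment. SAP 3.7 has parents keep the diary from T0 to T1, and the infant is randomized at T1 once the diagnosis is reconfirmed. Age at T0 is also derived: "Age (days) at baseline will be computed in terms of days elapsed from birth date to informed consent date" (SAP 6.2).

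**The concern.** Dividing by Week 1 crying does not adjust for it. Two diary weeks are imperfectly correlated, so an infant whose Week 1 value is unusually high tends to fall back and may reach the 50% cut without any treatment effect. If so, Week 1 crying predicts success in either arm, and a chance difference between arms in Week 1 crying moves the observed success rates. With 32-40 infants per arm and no stratification stated, such differences will occur, and nothing in the primary analysis takes them out. At stake are the precision of the one confirmatory comparison and how well its result stands up if the arms happen to differ at Week 1.

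**Working it through.** **1. The plan's own figure.** Inputs from SAP 3.6: 15% vs 50% success, 80% power, alpha 0.05 (sidedness not stated; two-sided assumed). The mean rate is 0.325.

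- Uncorrected: n = [1.960·√(2·0.325·0.675) + 0.842·√(0.15·0.85 + 0.50·0.50)]² / 0.35² = (1.298 + 0.517)² / 0.1225 = 26.9, so 27.
- With continuity correction: (26.9/4)·[1 + √(1 + 4/(26.9·0.35))]² = 32.4, so 33.

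The stated 33 per group is reproduced.

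**2. Is the planned test sound?** Exact binomial enumeration of the uncorrected chi-square gives 88.8% power at 33 per group and 87.5% at 32 (80 infants less 20% dropout, halved). Exact type I error at a 15% rate is 5.3% at either size.

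**3. How strongly does Week 1 predict success?** The documents give no SD and no correlation, so these are assumptions: bivariate normal log crying, correlation r between Week 1 and last week, and k = SD(Week 1)/SD(last week). The share of the variance of log change explained by Week 1 is

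(r − k)² / (1 + k² − 2rk), which is (1 − r)/2 when k = 1.

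| k | r = 0.3 | r = 0.5 | r = 0.7 |
|---|---|---|---|
| 1.3 | 0.52 | 0.46 | 0.41 |
| 1 | 0.35 | 0.25 | 0.15 |
| 0.7 | 0.15 | 0.05 | 0 |
| 0.5 | 0.04 | 0 | 0.07 (direction reversed) |

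High Week 1 values favour success only when r < k. With k = 1, r = 0.5 and 15% success overall, success is 3.8% at 1 SD below and 27% at 1 SD above mean log Week 1 crying.

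**4. Power at 15% vs 50%, 32 per arm.** Simulation with 2,500 trials per setting: chi-square against a logistic score test adjusted for log Week 1 crying and one non-prognostic covariate.

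| k | r | Unadjusted | Adjusted | Change |
|---|---|---|---|---|
| 1 | 0.3 | 87.2% | 92.8% | +5.6 |
| 1 | 0.7 | 87.8% | 89.9% | +2.1 |
| 0.7 | 0.3 | 86.3% | 88.4% | +2.1 |
| 0.7 | 0.5 | 87.2% | 87.1% | −0.1 |
| 0.7 | 0.7 | 87.7% | 87.0% | −0.7 |
| 0.5 | 0.3 | 87.5% | 88.0% | +0.5 |
| 0.5 | 0.5 | 87.3% | 87.0% | −0.3 |
| 0.5 | 0.7 | 87.2% | 88.1% | +0.9 |

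At k = 1.3 the gain is 7-8 points over the same range of r. Each simulated power has a standard error of about √(0.87·0.13/2500) = 0.7 points. A linear model with robust SE at 33 per group and k = 1 gave gains of 4.1, 3.1 and 1.4 points for r = 0.3, 0.5 and 0.7. Taken together, the k = 1 gain is about 2-5 points.

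**5. Chance imbalance.** One standard error of the Week 1 difference is √(2/32) = 0.25 SD. With k = 1 it moves the success rate by d·√((1 − r)/2) on the normal-quantile scale. With no true effect and 30% success, that is a difference of 3-5 points for r = 0.7 to 0.3; a two-standard-error imbalance gives 7-10 points. The unadjusted standard error of the difference is √(2·0.3·0.7/32) = 11.5 points. In null simulations with k = 1, the chi-square rejected 9-10% of the time at 30% success (7-13% at 15%) when the Week 1 imbalance exceeded 1.5 standard errors, and 3-5% when it was below 0.5.

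**The case against.** The strongest reply is that nothing is broken. Week 1 crying is the denominator of every infant's outcome. Regression to the mean raises success in both randomized arms alike. Chance imbalance is part of the sampling error the chi-square already allows for, and the differences in step 5 average to zero over randomizations. Power exceeds the planned 80%. The chi-square is transparent, agrees with the Protocol and matches the basis of the sample size. All of this stands.

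A reader might therefore infer from the missing covariate that the success comparison is biased, that type I error is inflated, or that the trial falls short of its planned power. The documents support none of these. The raised rejection rates in step 5 apply only to trials with a large imbalance and are balanced by lower rates elsewhere.

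It is also fair to say that the gain rests on the SD ratio. Reconfirming the diagnosis at T1 may narrow Week 1 crying, while last-week crying is unselected, so k below 1 is plausible and the benefit may be nil.

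What the reply does not remove is that a potentially strong pre-treatment predictor is in hand, costs almost nothing to use, and appears in no planned analysis of the primary endpoint. The planned power also holds only at the planned rates. With k = 1 and r = 0.3-0.7, at 15% vs 45% (a scenario chosen here, not in the SAP), the chi-square has 77% power and the adjusted test 80-85%.

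**Conclusion.** The point holds as one of efficiency and robustness, not of validity. At the SAP's rates, with 32 per arm and r = 0.3-0.7, adjustment for log Week 1 crying changes power by about +2 to +5 points with equal log SDs, about −1 to +2 if the Week 1 SD is 0.5-0.7 of the last-week SD, and +7 to +8 if it is 1.3 times as large. These ranges rest on a log-normal model and on assumed values of r and k. Age does not share the support for Week 1 crying: nothing in the documents or the calculations shows that it predicts success.

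**What to change.** In SAP 6.5.1, pre-specify an analysis of success adjusted for the log of the Week 1 mean crying duration. Define the covariate explicitly as the T0-T1 diary mean that forms the endpoint's denominator, because SAP 6.1 defines baseline as visit T0. Use a logistic score test or a robust-SE model. Avoid the likelihood-ratio test, which rejected 5.8-7.2% of the time under the null at 33 per group; the robust-SE linear model gave 4.6-5.7% there, and the score test 4.8-6.0% at 32. Report the standardised risk difference with its confidence interval beside the unadjusted chi-square, since a logistic odds ratio is conditional on the covariate.

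Make this the primary test or, at minimum, enter it under 6.5.2. Age at T0 is optional. If outcomes by arm have already been seen, label the adjusted analysis as not pre-specified.

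The endpoint and data collection do not change. The cost is a short SAP edit, some extra analysis work and a result that depends on a model, with possibly little or no gain if Week 1 crying proves weakly prognostic.

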## 6. DEFINITION AND GENERAL METHODOLOGY

### 6.1. GENERAL METHODOLOGY

All statistical tables, listings and figures will be produced using SAS® for Windows release 9.4 (64-bit) or later (SAS Institute Inc., Cary, NC, USA). Continuous data will be summarized by mean,

	Statistical Analysis Plan
	Sponsor:
	Protocol number:

standard deviation (SD), median, 1st and 3rd quartile, minimum and maximum. Categorical data will be presented by absolute and relative frequencies (n and %) or contingency tables.

Percentages will be computed considering patients with non-missing information, if not differently specified.

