### 6.5.3. Secondary efficacy analysis

- Number of cries

Number of cries are collected daily in the diary during the entire study period.

Weekly mean of cries will be defined as the mean number of cries reported in the “Evaluation of behavior” section during the week (i.e. number of episodes/number of days with episodes) and will be described by means of descriptive statistics for continuous data.

Mean changes from baseline (i.e. mean of the first Week) to the mean of the selected week will be analyzed too.

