#### **6.5.4. Exploratory efficacy analysis**

Not Applicable.

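### Crying duration is tested between groups only as a 50% responder chi-square; no risk difference, confidence interval or comparison on the duration scale is pre-specified

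*SAP*

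**What the plan says.** SAP 6.5.1 defines success as a reduction of at least 50% from Week 1 (T0 to T1) to the last week (T4 to T5). The success proportion is "summarized by means of descriptive statistics for categorical data and analyzed by means of a Chi-Square test". The protocol synopsis (Statistical methods, Primary variable) names the same test.

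For duration itself, SAP 6.5.1 describes weekly means and adds: "Mean changes from baseline (i.e. mean of the first Week) to the mean of the selected week will be computed as well". No test, model, between-group difference or interval is attached to them. SAP 6.5 has efficacy data summarised by treatment. For continuous data, SAP 6.1 lists mean, SD, median, quartiles and range. For categorical data it says: "Categorical data will be presented by absolute and relative frequencies (n and %) or contingency tables". SAP 6.5.2, "Sensitivity analysis on primary endpoint", and SAP 6.5.4, "Exploratory efficacy analysis", are both marked not applicable.

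The one continuous between-group test in the SAP concerns another variable. Section 6.5.3 plans a t-test on the change in weekly mean number of cries, with a switch to Wilcoxon if the data are not normal. Section 1.1 says the reduction in number of cries will not be evaluated, because the eCRF does not hold the information.

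**The concern.** SAP 2.1 words the primary objective as one of estimation, yet the named output is two percentages and a p-value. The size of the treatment effect and its uncertainty are left for the reader to work out.

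Duration is recorded daily throughout, and Week 1 is complete before randomisation at T1 (SAP 3.2 and 3.7). Each infant therefore has a last-week/Week 1 ratio in principle, and the primary analysis reduces it to yes or no at 0.5. A 49% reduction then counts the same as no change, and a 51% reduction the same as complete resolution. At stake are an effect size with its precision and some power for a supportive analysis. If a continuous comparison is wanted later, its form would be chosen after the data are seen.

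**Working it through.** **Inputs.** SAP 3.6 gives "15% in the Placebo group and 50% in the treatment group", alpha 0.05, 80% power, 33 per group, and 80 infants in total. Sidedness is not stated; two-sided is assumed.

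**1. The plan's own figure.** With mean proportion 0.325:

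n = [1.96√(2 × 0.325 × 0.675) + 0.842√(0.15 × 0.85 + 0.50 × 0.50)]² / 0.35² = (1.298 + 0.517)² / 0.1225 = 26.9, so 27 per arm.

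Continuity-corrected: (26.9/4) × [1 + √(1 + 4/(26.9 × 0.35))]² = 32.4, so 33 per arm. The stated 33 is reproduced by the corrected formula.

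**2. Power of the planned test.** Summing binomial probabilities over all tables that reject at 0.05:

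| Per arm | Uncorrected | Continuity-corrected |
|---|---|---|
| 33 | 88.8% | 82.0% |
| 40 | 93.3% | 89.7% |

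At 33 per arm neither version falls short of 80%. The SAP does not say which version will be used.

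**3. The interval the plan does not name.** Newcombe's method combines the Wilson limits of each arm. At 33 per arm these are 0.066 to 0.307 for 15% and 0.339 to 0.661 for 50%.

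- Lower: 0.35 − √[(0.500 − 0.339)² + (0.307 − 0.150)²] = 0.124
- Upper: 0.35 + √[(0.661 − 0.500)² + (0.150 − 0.066)²] = 0.532

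That is about 12 to 53 points. At 40 per arm it is about 15 to 52.

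**4. What dichotomising may cost.** The documents give no SD, distribution or correlation for duration, so two assumed models were used, both with success held at 15% and 50%.

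- *Normal percent reduction, equal SDs.* The implied shift is z(0.50) − z(0.15) = 1.04 SD. Power at 33 per arm is Φ(1.036 × √(33/2) − 1.96) = Φ(2.25) = 98.8%, against 87.7% for the uncorrected chi-square by the same kind of approximation. If the active success rate were 40%, the figures are 88.9% and 62.8%.
- *Log-normal durations, ratio independent of Week 1.* This was simulated at 33 per arm, 10,000 trials per cell, 12 cells. Log-ratio SD was 0.5 or 1.0, log-Week 1 SD 0.3 or 0.5, and 0, 20 or 40% of successes had a last week of zero crying.

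| Analysis | Power |
|---|---|
| Chi-square, uncorrected | 88-89% |
| Rank-sum on the ratio | 97-98% |
| Raw change, t-test | 84-96% |
| Raw ANCOVA | 83-96% |

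Raw ANCOVA differs from raw change by only −1 to +3 points. The gain comes from leaving the ratio uncut, not from a covariate, and raw ANCOVA may not beat the chi-square. Type I error of the rank-sum test in four null cells was 0.045 to 0.050.

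**5. Number of cries, if it is analysed.** The variance of the ANCOVA estimate relative to the change score is k²(1 − r²)/(1 + k² − 2rk), where k is last-week SD over Week 1 SD and r their correlation. With k = 1 it reduces to (1 + r)/2, giving 0.65 to 0.90 for assumed r of 0.3 to 0.8. With k = 1.3 it is 0.805 to 0.997, so the gain can vanish.

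**The case against.** The strongest reply is that the information is not absent. SAP 6.1, 6.5 and 6.5.1 together give the mean change in duration by arm, and n and % by arm give the risk difference and its interval by arithmetic. That stands. A reader might infer that the report would not show how much crying fell relative to placebo. The documents do not support this, because the two arms' changes will be tabulated and can be subtracted. What is missing is a pre-specified estimate, interval and comparison.

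A reader might also build a borderline table in which p is just below 0.05 while the interval reaches zero. Such an example depends on the uncorrected chi-square. The SAP does not specify the version, and its sample size matches the corrected one, so nothing here relies on it.

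A third reply is that a responder endpoint fixed in both documents, and used to size the trial, is a legitimate primary. It is, and no change to it is proposed. It is also fair that the power gains rest on assumed distributions. The risk-difference interval does not.

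Finally, the protocol is available only as a synopsis and no table shells are supplied, so the omission is established only for these documents.

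**Conclusion.** The omission is real, and worth correcting as a cheap improvement. The only between-group inference on crying duration is a chi-square on the 50% cut. It would be wrong to infer that the test is invalid or the trial underpowered: power at 33 per arm is 82% or 89%, depending on the correction.

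The loss has two parts. One is a stated effect with its precision, which at the planning rates means an interval of about 12 to 53 points. The other is the information lost at the cut: roughly 97-99% power for a comparison on the uncut scale against 88-89% for the uncorrected chi-square, under the assumed models only. No covariate gain is claimed for duration.

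Two matters are preconditions rather than part of this finding. First, SAP 6.5.1 computes the daily value as "duration/number of cries during the day", which is minutes per cry and is undefined on a day without cries, whereas the protocol synopsis describes mean daily crying duration and keeps zeros. Second, SAP 6.1 sets baseline at visit T0, whereas 6.5.1 uses the Week 1 mean.

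**What to change.** 1. Keep the chi-square as primary. Report the risk difference with a 95% Newcombe interval.
2. State whether duration means total crying minutes per day or minutes per cry, give a rule for days and weeks without cries, and name the Week 1 mean as the baseline for this variable. Then pre-specify one supportive analysis: a Wilcoxon rank-sum test on each infant's last-week/Week 1 ratio, with the Hodges-Lehmann shift in that ratio and its 95% CI. If zeros are kept, a week without crying ranks as ratio 0 and needs no log offset. The estimate should match the test: under the log-normal model, a raw Week 1-adjusted mean difference had an interval including zero, while the rank test was significant, in about 2% to 16% of simulated trials.
3. Reconcile SAP 1.1 with 6.5.3 on number of cries. Only if that variable is analysed, state how days without cries count, since 6.5.3 uses "number of episodes/number of days with episodes". Then replace the t-test/Wilcoxon switch by ANCOVA of the last-week mean on treatment and the Week 1 mean.

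The cost is SAP wording, one interval and one or two extra supportive analyses. For duration these use diary data already collected; item 3 depends on the cry counts being available. The primary test and alpha do not change. If the data have already been analysed, the risk difference and its interval can still be reported, and the duration comparison should be labelled post hoc.

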### 6.5.2. Sensitivity analysis on primary endpoint

Not Applicable.

### 6.5.3. Secondary efficacy analysis

- Number of cries

Number of cries are collected daily in the diary during the entire study period.

Weekly mean of cries will be defined as the mean number of cries reported in the “Evaluation of behavior” section during the week (i.e. number of episodes/number of days with episodes) and will be described by means of descriptive statistics for continuous data.

Mean changes from baseline (i.e. mean of the first Week) to the mean of the selected week will be analyzed too.

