## 1. INTRODUCTION

### 1.1. CHANGES FROM THE STUDY PROTOCOL

Reduction of the number of cries from baseline to the end of study (after 28 days), presence of infantile colic at the end of study (after 28 days), reduction of the number of regurgitations and vomiting episodes will not be evaluated since information about these secondary objectives is not collected in the eCRF.

The analysis of Bifidobacterium BB-12® effect on gut microbiota, on the fecal production of peptides from innate immune system (Calprotectina,  $\beta$ -defensin 2, LL37) and on fecal short chain-fatty acids production (butyrate and propionate) will be provided by the center to Sponsor and reported in a separate document.

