### 2.2. SECONDARY OBJECTIVES

- Reduction of the number of cries from baseline to the end of study (after 28 days) and presence of infantile colic at the end of study (after 28 days);
- reduction of the number of regurgitations and vomiting episodes;
- number of infections of the respiratory system, gastrointestinal system, urinary system or skin during the study period;
- evacuative frequency;
- consistency of the fecal mass;

	Statistical Analysis Plan
	Sponsor:
	Protocol number:

- Bifidobacterium BB-12® effect on gut microbiota, on the fecal production of peptides from innate immune system (Calprotectina,  $\beta$ -defensin 2, LL37) and on fecal short-chain fatty acids production (butyrate and propionate).

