#### SECONDARY EFFICACY PARAMETERS

- Number of cries from baseline to the end of study (after 28 days) and presence of infantile colic at the end of study (after 28 days).
- Number of regurgitation and vomit.
- Number of infections of the respiratory system, gastrointestinal system, urinary system or skin during the study period.
- Daily evacuative frequency.
- Daily consistency of the fecal mass, evaluated through Bristol stool scale.

	Statistical Analysis Plan
	Sponsor:
	Protocol number:

- Bifidobacterium BB-12® effect on gut microbiota, on the fecal production of peptides from innate immune system (Calprotectina,  $\beta$ -defensin 2, LL37) and on fecal short chain-fatty acids production (butyrate and propionate).

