#### HANDLING OF MISSING DATA/IMPUTATION RULES/CENSORING RULES

Not Applicable.

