## Statistical Analysis Plan

Sponsor:

Protocol number:

Moreover, in order to compare the two groups of patients, a t-test on the change of weekly mean of cries at last Week will be performed. In case of data not normally distributed, a Wilcoxon/Mann-Whitney test will be used.

- Number of infections of the respiratory system, gastrointestinal system, urinary system or skin during the study period.

Number of infections will be described on the ITT population, even if infections are defined using safety parameter. In fact, an infection will be defined as an Adverse Event with SOC equal to "Infections and Infestations".

The frequency and proportion of patients who reported at least one infection will be summarized and presented by category, System Organ Class and Preferred Term.

- Evacutive frequency

Frequency and consistency of stools are collected daily in the diary.

Stool frequency will be evaluated as the mean of total daily stools reported per week. Mean changes from baseline (i.e. mean of the first Week) to the mean of the selected week will be analyzed.

Summary statistics of mean stool frequency per week will be provided by means of descriptive statistics for continuous data.

- Consistency of the fecal mass

Stool consistency will be evaluated as the number and the proportion of patients who reported at least one stool sample of each type per week, according to Bristol scale. Patients could report more than one stool consistency per day (according to the number of daily stools): all the information collected will be analyzed.

Other data from patients' diary will be analyzed:

- Infant's mood

Infant's mood (calm, asleep, agitated, irritable) is collected daily in the diary and will be evaluated as the number and the proportion of infants who reported at least one mood of each type per week.

- Infant's sleep

Duration of sleep (in minutes) will be collected daily in the diary during the entire study period. The average daily duration will be defined as the mean duration of all sleeps during the day (i.e. sum of episodes' duration/number of sleeps during the day).

Weekly mean will be defined as the mean of the calculated average daily durations during the selected week and will be described by means of descriptive statistics for

	Statistical Analysis Plan
	Sponsor:
	Protocol number:

continuous data. Mean changes from baseline (i.e. mean of the first Week) to the mean of the selected week will be analyzed too.

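### The weekly mean of cries ignores cry-free days and is undefined for a cry-free week, and the SAP both drops this endpoint and tests it

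*SAP*

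**What the plan says.** SAP 6.5.3, under number of cries, states: "Number of cries are collected daily in the diary during the entire study period". The weekly mean, taken from the diary's Evaluation of behavior section, is "number of episodes/number of days with episodes". For the group comparison, "a t-test on the change of weekly mean of cries at last Week will be performed", with a Wilcoxon/Mann-Whitney test if the data are not normal. No other secondary endpoint in 6.5.3 has a named between-group test.

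The SAP 6.1 entry headed "HANDLING OF MISSING DATA/IMPUTATION RULES/CENSORING RULES" is marked as not applicable, and so is the entry on drop-outs. No rule covers a day or a week without cries. The protocol synopsis (Statistical methods) does keep zero values in the computation, but says so only for crying duration.

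SAP 1.1 names the reduction in number of cries from baseline to day 28 among the secondary objectives that "will not be evaluated since information about these secondary objectives is not collected in the eCRF". SAP 2.2 and 5.1 still list the endpoint.

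**The concern.** The objective is a fall in the number of cries. An infant can achieve that by crying less often on the days it cries, by having fewer days with any crying, or both. A denominator limited to days with episodes removes the second route. An infant with no cries in the last week, the best possible result, has no value at all and would fall out of the test.

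Separately, one section of the SAP says the endpoint is not analysed and another defines and tests it. Reporting the result and omitting it are then both consistent with the plan, so the choice could be made after the data are seen.

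**Working it through.** **The plan's own figure.** The only design figure is 33 per group (SAP 3.6: 15% versus 50% success, 80% power, alpha 0.05). It reproduces as 33 with a two-sided, continuity-corrected comparison of two proportions, and as 27 without the correction. It belongs to the primary endpoint and does not enter this point, except that 33 per arm is used below as the simulation size. The documents give no cry rates, so every rate below is an assumption.

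**1. Example weeks, 4 cries on each crying day**

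| Crying days | SAP: episodes / days with episodes | All days: episodes / 7 |
|---|---|---|
| 7 | 28/7 = 4.0 | 4.0 |
| 3 | 12/3 = 4.0 | 1.71 |
| 1 | 4/1 = 4.0 | 0.57 |
| 0 | 0/0, undefined | 0 |

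An infant going from 7 crying days to 1 shows no change under the SAP formula. Over all days the change is 0.57 − 4.0 = −3.43 cries a day (−86%).

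**2. General form.** Let m be the mean cries per crying day and p the share of crying days. Cries per day are m × p, while the SAP measures m. With equal m in both arms, the SAP difference is 0 whatever happens to p. With equal p, the SAP difference is 1/p times the difference in cries per day; at p = 5/7 that is 1.40.

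**3. Poisson daily counts.** At rate L, the mean on days with at least one cry is L/(1 − exp(−L)): 0.5 gives 1.271, 1 gives 1.582, 2 gives 2.313, 3 gives 3.157, 4 gives 4.075, 6 gives 6.015.

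| Cries per day, arm 1 vs arm 2 | True difference | SAP difference | Shrinkage |
|---|---|---|---|
| 0.5 vs 2 | 1.50 | 1.04 | 31% |
| 1 vs 3 | 2.00 | 1.58 | 21% |
| 2 vs 4 | 2.00 | 1.76 | 12% |
| 3 vs 6 | 3.00 | 2.86 | 5% |
| 4 vs 8 | 4.00 | 3.93 | 2% |

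**4. Undefined weeks.** The probability of a cry-free week is exp(−7L): 0.1% at 1 cry a day, 3.0% at 0.5 (about 1 infant in 33), 17% at 0.25 and 50% at 0.1.

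**5. Power.** Simulation of 4000 runs, 33 per arm, t-test on change from baseline. Assumed baseline: 5 cries per crying day on 95% of days, with a between-infant lognormal SD of 0.3. Values are active versus placebo in the last week.

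| Scenario | True difference | SAP difference | Power, all days | Power, SAP |
|---|---|---|---|---|
| A: m 3 vs 3, p 3/7 vs 5/7 | 0.85 | 0.00 | 65% | 5% |
| B: m 2.5 vs 3, p 3/7 vs 5/7 | 1.06 | 0.49 | 83% | 34% |
| C: m 2.5 vs 3.5, p 5/7 in both | 0.72 | 1.01 | 57% | 93% |
| D: m 2.5 vs 3.5, p 6/7 vs 6.5/7 | 1.10 | 1.00 | about 93% | about 91% |

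In A, 1.9% of active-arm infants have no value, against 0.02% on placebo. Repeat runs moved the power figures by at most about 4 percentage points. With Poisson counts, power for all days versus SAP is 90% vs 64% (0.5 vs 2 a day), 96% vs 93% (2 vs 4), 48% vs 45% (3 vs 4) and 40% vs 39% (4 vs 5).

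**6. The contradiction.** SAP 1.1 removes the endpoint because the eCRF lacks the data. SAP 6.5.3 says the diary holds daily counts, then defines the variable and names a test. SAP 6.5.1 needs a count as well: the average daily duration is the "mean duration of all cries recorded during the day in the" Evaluation of crying section, computed as a sum divided by the day's number of cries. So 6.5.1 and 6.5.3 cite differently named diary sections, and the SAP does not say whether either count reached the database. SAP 1.1 is the current statement of departures from the protocol, not a log of superseded SAP text.

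**The case against.** The strongest reply is that the damage may be negligible. If these infants cry nearly every day, the two definitions almost coincide, as scenario D and the higher Poisson rates show. Scenario A gives zero by construction, because the whole effect is placed where the formula cannot see it. The 0/0 case is rare unless rates fall to about 0.5 a day or lower. All of this stands: the wording is certainly at fault, but the size of the effect is unknown.

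Scenario C can also be described as a sound estimate of a different quantity, cries per crying day, with no inflation of type I error shown. That is fair. It is still not the reduction in number of cries that SAP 2.2 names.

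Perhaps diary days were meant. The SAP does not say so, and its stool-frequency definition in the same section carries no restriction to days with events.

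On the contradiction, SAP 2.2 and 5.1 largely restate the protocol's endpoints, and 1.1 can be read as qualifying them, so the real clash is 1.1 against 6.5.3. Because 6.5.1 cannot be computed without a count, 1.1 may well be the drafting error. The different diary section names cannot be shown to be a discrepancy without the diary. These are reasonable inferences, but the SAP leaves the reader to make them. If 1.1 governs, the denominator question falls away, which is why the status of the endpoint must be settled first.

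**Conclusion.** Both parts hold. Followed exactly, the formula in SAP 6.5.3 does not measure the number of cries per day and gives no value for a cry-free week. The current SAP also both drops and tests the endpoint.

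The numerical effect depends wholly on how often cry-free days occur. Under the assumptions shown, it runs from a 2% smaller difference to complete loss of the effect, and it can also enlarge the difference by 40%, so the definition cannot be defended as conservative. The contradiction needs resolving at any cry rate.

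The change should be made, but it concerns one secondary endpoint. The primary test and the sample size do not depend on it.

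**What to change.** - Define the weekly mean as total cries in the week divided by the number of days with a completed diary entry. Cry-free days count as 0, so a fully recorded cry-free week scores 0. Unrecorded days are left out of numerator and denominator.
- Establish whether the daily counts are in the database. If they are, remove number of cries from the not-evaluated list in SAP 1.1 and name the diary section used. If they are not, delete the 6.5.3 analysis. Align SAP 2.2 and 5.1 with the decision.
- Do this before unblinding. If the data are already unblinded, report the corrected measure as a disclosed post-hoc reanalysis.

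The cost is two or three SAP sentences and a small code change. The one practical demand is that the dataset must tell a cry-free day from an unrecorded one.
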